11.2.1. Tumor Imaging

Tumor imaging by chest/abdomen/pelvic CT scan or MRI: the baseline tumor assessment by CT scan or MRI has to be performed within 3 weeks prior to the treatment start; during the treatment period (irrespectively of cycles duration) the first assessments will be performed 6 weeks (between days 42 and 48) after first drug administration, **the second one 3 months (between days 92 and 98) after first drug administration**, the following ones every 6 weeks (between days 42 and 48) after the previous one (or whenever a clinical

> Tiziana Life Sciences, PLC - Confidential Page 58 of 101

Milciclib maleate (PHA-848125AC)	CDKO-125a-006-P4
Protocol for Study CDKO-125a-006	09 March 2017

deterioration will be observed) and at end of last cycle (if not done in the previous 4 weeks). For patients with responding tumors (complete or partial response), response confirmation must be performed no less than 4 weeks after the criteria for response are first met.

In addition, in patients withdrawn from study treatment for causes other than disease progression, tumor response will have to be reassessed at the time of study drug discontinuation, unless a tumor assessment was performed within the previous 4 weeks. In these patients, regular tumor imaging assessments are to be performed every 6 weeks during follow-up, until PD or until a new antitumor therapy starts.

The same method and technique (CT scan, spiral CT scan or MRI) should be used to characterize each identified and reported lesion at baseline and during follow-up. Imaging-based evaluation, over clinical examination, is the required technique when both could be used to assess the antitumor effect of the treatment.

CT scan is the desirable method for lesion measurement. CT scans should have a maximum slices thickness of 5 mm and a minimum size for a measurable lesion is twice that: 10 mm (even if slice thickness is <5 mm). If scanners with slice thickness > 5 mm are used, to qualify for a measurable lesion, the minimum lesion size must have a longest diameter twice the actual slice thickness. MRI is acceptable (but not for lung lesions), provided that the size of the measurable lesion is twice the slice thickness of the MRI.

All patients' files and scans must be available for source verification.

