CR = complete response, PR = partial response, SD = stable disease, PD = progressive disease, and NE = inevaluable. ^a If a CR is truly met at first time point, then any disease seen at a subsequent time point, even disease meeting PR criteria relative to baseline, makes the disease PD at that point (since disease must have reappeared after CR). Best response would depend on whether minimum duration for SD was met. However, sometimes 'CR' may be claimed when subsequent scans suggest small lesions were likely still present and in fact the patient had PR, not CR at the first time point. Under these circumstances, the original CR should be changed to PR and the best response is PR.

Patients with a global deterioration of health status requiring discontinuation of treatment without objective evidence of disease progression at that time should be reported as "symptomatic deterioration" (see Study Manual specific data collection instructions). Of note, every effort should be made to document the objective progression even after discontinuation of treatment. Symptomatic deterioration is not a descriptor of an objective response: it is a reason for stopping study therapy. The objective response status of such patients is to be determined by evaluation of traget and non-target disease.

In some circumstances, it may be difficult to distinguish residual disease from normal tissue. When the evaluation of a CR depends upon this determination, it is recommended that the residual lesion be investigated by fine needle aspirate or biopsy before assigning a status of CR.

For equivocal findings of progression (e.g. very small and uncertain new lesions; cystic

Tiziana Life Sciences, PLC - Confidential Page 64 of 101 changes or necrosis in existing lesions), treatment may continue until the next scheduled assessment. If at the next scheduled assessment, progression is confirmed, the date of progression should be the earlier date when progression was suspected.

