12.2. Definition of Analyzed Study Populations

For the purpose of the analysis, the following patient populations are defined and the endpoints, to be analyzed in these populations, are specified:

- *Screened Patients:* This population will include all subjects who are screened about their eligibility for the trial, regardless of whether or not they will be enrolled in the study. This population will be evaluated in the analysis of patients' disposition.
- *Enrolled Patients:* This population will include all subjects who are enrolled in the trial, regardless of whether subjects receive the study drug or not. This population will be evaluated in the analysis of patients' disposition.
- *Treated Patients:* The treated patient population consists of all enrolled patients who actually receive at least one study drug administration. This population will be evaluated in the analysis of patient disposition, baseline characteristics, treatment efficacy and safety and treatment exposure.
- *Patients Evaluable for Efficacy Analysis:* This is the patient population for the primary efficacy analysis of PFS-3 rate and consists of all treated patients who fulfill the following additional conditions:
 - They have received histological confirmation of thymic carcinoma by an Independent Review Committee
 - They receive at least 80% of drug in the first two cycles overall.
 - They have baseline and ≥1 on-treatment tumor/oncologic assessment(s) or die before tumor re-assessment.

If deemed of clinical interest, patient disposition, baseline characteristics, treatment efficacy and safety and treatment exposure will be analyzed also in this population.

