12.3.4. Efficacy Analyses

Primary Efficacy Endpoint

For the primary efficacy analysis, the primary endpoint, *i.e.* the PFS-3 rate, will be calculated as the proportion of evaluable patients (see Section 12.2) known to be alive and progression-free at \geq 3 months since study treatment start out of the total number of evaluable patients (see Section 4.2.1). Decision rules will be applied in the primary efficacy analysis as described in Section 12.1, i.e.:

- At least 4 / 17 evaluable patients alive and progression free at \ge 3 months are required not to early terminate the trial and reject the drug at the end of the first step.
- At least 14 / 54 evaluable patients alive and progression free at \geq 3 months are required at the end of the second step to reject the null hypothesis of a PFS-3 rate as low as 17%, at the 1-sided α -level of 0.05.

Supportive analyses of the primary endpoint will include the estimation of the PFS-3 rate together with its exact, two-tail, 95% confidence interval and the estimation of the PFS curve by the Kaplan-Meier method [43] in both the evaluable and the treated patient population.

Other Efficacy Endpoints

The secondary efficacy endpoints outlined in section 4.2.2 and including the confirmed objective response rate, the disease control rate, the duration of response and the overall survival will be analyzed in both the evaluable and the treated patient population as follows:

Objective tumor response rate: Point and 95% confidence interval estimates will be calculated for the objective tumor response rate (confirmed CRs or PRs). The analysis will

Tiziana Life Sciences, PLC - Confidential Page 77 of 101 be performed in the evaluable and in the treated patient populations. The estimates of the rates of unconfirmed tumor objective responses will also be provided and considered as supportive.

Disease control rate: Point and 95% confidence interval estimates will be calculated for the disease control rate (confirmed CRs / PRs and SD \ge 6 weeks). The analysis will be performed in the evaluable and in the treated patient populations.

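### The primary PFS-3 denominator drops and replaces living patients with no on-treatment assessment instead of counting them as non-successes, which can only push the tested rate upward

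*Protocol*

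**What the plan says.** Section 12.2 says of the evaluable set: "This is the patient population for the primary efficacy analysis of PFS-3 rate". Treated patients enter it on three further conditions: central confirmation of thymic carcinoma, "They receive at least 80% of drug in the first two cycles overall", and "They have baseline and ≥1 on-treatment tumor/oncologic assessment(s) or die before tumor re-assessment". The synopsis repeats all three. Sections 12.1 and 12.3.4 apply both decision rules, at least 4/17 and at least 14/54, to this set, and enrolment runs until 54 evaluable patients are reached.

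Section 12.3.4 defines a success as an evaluable patient "known to be alive and progression-free at" 3 months or later. Inside the set, an unknown status is therefore not a success.

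On assessments, section 11.2.1 states that "the first assessments will be performed 6 weeks (between days 42 and 48) after first drug administration". For patients withdrawn for reasons other than progression, it also says that "tumor response will have to be reassessed at the time of study drug discontinuation" unless a scan was made in the previous 4 weeks, and it asks for 6-weekly imaging afterwards. Section 11.2.1.6 foresees patients with "global deterioration of health status requiring discontinuation of treatment without objective evidence of disease progression" and adds: "Symptomatic deterioration is not a descriptor of an objective response: it is a reason for stopping study therapy".

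**The concern.** The two rules pull in opposite directions. The success definition is conservative, because a patient whose status at 3 months is not documented is not a success. The evaluability condition acts first and takes some of those patients out of the denominator before that rule can reach them. Since enrolment continues to a fixed number of evaluable patients, each one removed is replaced.

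Membership of the primary set thus depends on what happens after treatment starts. None of the removed patients is a documented success, and those who stopped because they were deteriorating are likely failures. Both the stage 1 stop/go decision and the final test use this denominator. The design spends almost all of its 5%, so even a small loss takes the error rate above nominal.

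**Working it through.** **Inputs.** Stage 1: 17 patients, stop at 3 or fewer successes. Final: 54 patients, at least 14 successes. Null rate 0.17, target 0.33, one-sided 0.05, power 0.80 (section 12.1). First scan on days 42-48 (11.2.1). At least 80% of drug in the first two cycles (12.2).

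**Step 1: reproduce the design.** The probability of declaring the drug interesting at true rate p is

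P(p) = sum over x = 4 to 17 of Bin(x; 17, p) × Pr[Bin(37, p) ≥ 14 − x].

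- P(0.17) = 0.0496 and P(0.33) = 0.806.
- Early termination at 0.17: 0.675. Continuation at 0.33: 0.863.
- Expected size at 0.17: 17 + 37 × (1 − 0.6749) = 29.0.

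All agree with the protocol. The margin below 5% is only 0.0004.

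**Step 2: who is lost through this condition alone.** Two cycles contain 14 dosing days, and 0.80 × 14 = 11.2, so 12 full doses meet the drug rule. Dosing runs on days 1-7 and 15-21, so the twelfth dose falls on day 19. A patient with confirmed histology who stops between about day 19 and day 42 meets the other two conditions, and the third decides:

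- has a qualifying assessment: in the set, success or not as documented;
- died before re-assessment: in the set, not a success;
- alive without a qualifying assessment: out of the set and replaced.

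**Step 3: effect on the tested rate.** Let d be the share of otherwise qualifying patients lost in the third way, and assume all are failures. Of N such patients there are 0.17 × N successes, but the denominator is (1 − d) × N, so the tested rate is 0.17 / (1 − d). Putting that rate into P and into the stage 1 stopping probability gives:

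| Assumed d | Tested rate | Type I error | Early stop |
|---|---|---|---|
| 0 | 17.0% | 4.96% | 0.675 |
| 1% | 17.2% | 5.3% | 0.668 |
| 3% | 17.5% | 6.1% | 0.653 |
| 5% | 17.9% | 7.0% | 0.637 |
| 10% | 18.9% | 10.0% | 0.596 |

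At the final boundary with d = 10%, 54 evaluable patients correspond to 54 / 0.90 = 60 patients. A result of 14/54 = 25.9% is then 14/60 = 23.3% once the 6 lost patients are counted.

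The documents do not give d, so the values in the first column are assumptions.

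**The case against.** The strongest reply is that the protocol already directs most early stoppers to an assessment. Section 11.2.1 asks for a scan at discontinuation, a scan at the end of the last cycle if none was made in the previous 4 weeks, and 6-weekly imaging until progression or new therapy. Section 10 defines treatment refusal as a patient who still accepts follow-up of disease status. Section 11.2.1.6 asks for every effort to document progression after stopping. A reader might infer that everyone who stops early for deterioration, toxicity or refusal leaves the denominator; these sections do not support that. The loss is confined to those for whom no qualifying assessment exists. It is not zero, since section 10 ends all evaluation on withdrawal of consent and some patients will be too ill, lost or missed.

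A reader might also infer that a scan after the last dose, even one showing progression, fails the on-treatment wording. That is one possible reading and not a stated rule. Section 11.2.1 lists the end-of-last-cycle scan among those of the treatment period, and a cycle includes 7 rest days. What stands is that the protocol leaves the matter open.

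Nor can one assert that the 17% reference is free of the same conditioning. It comes from a study that the protocol describes as reporting on evaluable patients (section 3.1), without saying how these were defined. If a follow-up assessment was required there, part or all of the correction in step 3 falls away.

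Finally, section 12.3.4 also gives the PFS-3 rate, with an exact interval, and the Kaplan-Meier curve in all treated patients. That helps a reader judge the selection. It is supportive only and carries no decision rule. It also lifts all three evaluability conditions at once, so it does not isolate this one.

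**Conclusion.** The point holds in limited form and should be fixed. A living patient without a qualifying assessment is dropped and replaced, and this pushes the rate used for both decisions upward relative to all confirmed treated patients. The direction follows from the definitions, because no dropped patient is a documented success.

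The size is not known. A type I error of 5.3% to 10.0% for a 1% to 10% loss rests on three assumptions: the share itself, that all those lost are failures, and that 17% is the right null for a set without this selection. It would be tempting to charge the full planned 15% of non-evaluable patients to this condition, which would give a tested rate of 20.0% and an error of 14.0%. The documents do not support that, because the 10%-15% allowance also covers unconfirmed histology (B3 thymoma may be enrolled but cannot be evaluable) and the 80% drug rule. With the discontinuation scan in place, the lower part of the range is plausible, but the protocol neither shows nor guarantees it.

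**What to change.** In section 12.2 and the synopsis, replace the third condition by a requirement for a baseline tumor assessment only. State that any patient in the set who is not documented alive and progression-free at 3 months counts as a non-success, whatever the reason. State also that any post-baseline assessment counts, whether made before or after the last dose. Keep the present evaluable set as a sensitivity analysis.

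The cost is one sentence in two places. The 17 and 54 patients and the 4/17 and 14/54 thresholds are unchanged, and the exact properties in step 1 then apply with respect to this condition. Fewer patients will be non-evaluable. The downside is a slightly less favourable reported rate.

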12.3. Analyses

12.3.1. Study Conduct and Subject Disposition

Patients' disposition will be presented in frequency distribution tables and individual data listings. All screened patients will be included in this evaluation. Violations of eligibility criteria at study entry as recorded in the relevant sections of the CRF will be documented. Reasons for stopping treatment will be summarized as frequency distribution in the treated patient population and, if clinically interesting, in other patient subsets (e.g. evaluable patients).

12.3.2. Baseline Characteristics

Descriptive statistics of the baseline characteristics will be generated in the treated patient population and, if clinically interesting, in other patient subsets (e.g. evaluable patients). Frequency distributions will be presented for the categorical / categorized variables. Tiziana Life Sciences, PLC - Confidential

Page 76 of 101

Milciclib maleate (PHA-848125AC)	CDKO-125a-006-P4
Protocol for Study CDKO-125a-006	09 March 2017

Summary statistics including mean, standard deviation, median, minimum, maximum and the number of assessed patients will be calculated, as appropriate, for the quantitative variables. Individual data will be presented in listings.

12.3.3. Treatment Administration/Compliance

The treatment exposure and the compliance with study treatment will be descriptively analyzed in the treated patient population and, if clinically interesting, in other patient subsets (e.g. evaluable patients). Descriptive statistics (e.g. min, max, mean, standard deviation, and median value) will be calculated on a per-patient basis for the following variables: the number of cycles administered, the overall duration of treatment, the actual and total doses administered, and the absolute and relative dose intensity. Frequency distributions of patients and/or cycles will be used to describe dose modifications, delays and omissions, as well as the reasons for deviation from the planned therapy. These data will be presented as reported in the relevant CRF sections.

12.3.4. Efficacy Analyses

Primary Efficacy Endpoint

For the primary efficacy analysis, the primary endpoint, *i.e.* the PFS-3 rate, will be calculated as the proportion of evaluable patients (see Section 12.2) known to be alive and progression-free at \geq 3 months since study treatment start out of the total number of evaluable patients (see Section 4.2.1). Decision rules will be applied in the primary efficacy analysis as described in Section 12.1, i.e.:

- At least 4 / 17 evaluable patients alive and progression free at \ge 3 months are required not to early terminate the trial and reject the drug at the end of the first step.
- At least 14 / 54 evaluable patients alive and progression free at \geq 3 months are required at the end of the second step to reject the null hypothesis of a PFS-3 rate as low as 17%, at the 1-sided α -level of 0.05.

Supportive analyses of the primary endpoint will include the estimation of the PFS-3 rate together with its exact, two-tail, 95% confidence interval and the estimation of the PFS curve by the Kaplan-Meier method [43] in both the evaluable and the treated patient population.

Other Efficacy Endpoints

The secondary efficacy endpoints outlined in section 4.2.2 and including the confirmed objective response rate, the disease control rate, the duration of response and the overall survival will be analyzed in both the evaluable and the treated patient population as follows:

Objective tumor response rate: Point and 95% confidence interval estimates will be calculated for the objective tumor response rate (confirmed CRs or PRs). The analysis will

Tiziana Life Sciences, PLC - Confidential Page 77 of 101 be performed in the evaluable and in the treated patient populations. The estimates of the rates of unconfirmed tumor objective responses will also be provided and considered as supportive.

Disease control rate: Point and 95% confidence interval estimates will be calculated for the disease control rate (confirmed CRs / PRs and SD \ge 6 weeks). The analysis will be performed in the evaluable and in the treated patient populations.

Time-to-event endpoints: For the other secondary endpoints, duration of response (in patients achieving a confirmed objective tumor response by RECIST version 1.1 criteria) and overall survival (OS), individual calculated times will be presented in patients' data listings together with the identification of censored vs. failure status. Kaplan-Meier curves will be estimated for OS in both the evaluable and the treated patient populations.

All collected efficacy data will be presented in individual patients' data listings.

12.3.5. Outcomes Research Analyses

Not applicable in this study.

12.3.6. Safety Analyses

Safety data will be evaluated in the treated patient population and, if clinically interesting, in other patient subsets (e.g. evaluable patients).

The adverse events (AEs) will be coded by the Medical Dictionary for Regulatory Activities (MedDRA) and their severity graded according to the NCI Common Terminology Criteria for Adverse Events (CTCAE) version 3.0. The MedDRA preferred term and system organ class (SOC) will be used to identify and group events in data listings and descriptive analyses. All reported baseline signs and symptoms and on-treatment adverse events will be reported in the patients' data listings. The analysis will address all the events that are recorded on treatment (i.e. from cycle 1, on). The raw incidence of each sign/symptom, of the subsets of events grouped by system organ class and, in general, the raw incidence of any AE, will be calculated. In this analysis, every patient will be accounted for on the basis of the worst CTCAE grade reported during the whole period, within the considered category (*e.g.* the analyzed sign/symptom or system organ class). The following subsets of AEs will also be specifically considered: serious AEs, AEs with CTCAE grade 3-5, AEs with a relationship to study treatment classified by the Investigator as possible or probable or definite and AEs reported as leading to discontinuation from treatment.

Raw incidence of death will be calculated. Deaths will also be described in terms of relationship to the study treatment and according to the time from treatment stop.

Laboratory test values will be graded according to the NCI CTCAE scale, v3.0, whenever possible. For each laboratory test included in the NCI CTCAE system, the incidence of Tiziana Life Sciences, PLC - Confidential Page 78 of 101 abnormalities will be evaluated by considering the worst occurrence for each patient throughout the whole treatment period. The frequency distributions of cycles according to the worst CTCAE grade will also be calculated for selected parameters, as clinically indicated. Preliminary conversions of reported values from the originally reported units to a set of predefined units will be applied to facilitate the comparison. For selected parameters descriptive analysis of shifts relative to baseline will be performed if deemed of clinical relevance. Coagulation tests will be evaluated with respect to the corresponding baseline values and to the recorded normal ranges. Urinary parameters will be documented in patient data listings.

Ophthalmologic examinations will be summarized in terms of normal / abnormal findings. Shift tables comparing patients' worst assessments after treatment initiation to the corresponding baseline assessments will be built.

All collected safety data (including vital signs, ECG, ophthalmologic evaluations, laboratory tests and adverse events) will be presented in individual patients' data listings. Identification of clinically relevant values and calculation of changes from baseline will be provided in the listings for those parameters and conditions deemed of clinical relevance.

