6.1. Subject Inclusion Criteria

Subjects must meet all of the following inclusion criteria to be eligible for enrollment into the study:

- 1. Signed and dated IRB/IEC-approved Informed Consent.
- 2. Histologically or cytologically proven diagnosis of unresectable B3 thymoma or thymic carcinoma recurrent or progressing after prior chemotherapy (only one prior systemic therapy allowed).
- 3. Presence of measurable disease defined as at least one lesion that can be accurately measured by CT scan in at least one dimension, as > 10 mm for non nodal lesions (longest diameter to be recorded) and ≥ 15 mm for lymph nodal lesions (short axis to be recorded). (CT scan is the desirable method for lesion measurement. Other measurement techniques [eg MRI] are acceptable [but not for lung lesions] provided that the size of the measurable lesion is twice the slice thickness of the MRI). Tumor lesions situated in a previously irradiated area, or in an area subjected to other loco-regional therapy, are usually not considered measurable unless there has been demonstrated progression in the lesion.
- 4. Age \geq 18 years.
- 5. ECOG performance status 0-1.
- 6. Estimated life expectancy of at least 3 months.
- 7. Negative pregnancy test (if female in reproductive years).

Tiziana Life Sciences, PLC - Confidential Page 38 of 101

Milciclib maleate (PHA-848125AC)	CDKO-125a-006-P4
Protocol for Study CDKO-125a-006	09 March 2017

- 8. Agreement upon the use of effective contraceptive methods (hormonal or barrier method of birth control, or abstinence) prior to study entry and for the duration of study participation, if men and women of child producing potential.
- 9. Adequate liver function:

•	Total S	erum B	ilirubin	\leq 1.5 x upper limit of normal (ULN)
	æ			

- Transaminases (AST/ALT) ≤ 2.5 ULN (if liver metastases are present, then ≤ 5 ULN is allowed)
- ALP ≤ 2.5 ULN (if liver and/or bone metastases are present, then ≤ 5 ULN is allowed).

10. Adequate renal function:

• Serum Creatinine ≤ ULN or

Creatinine Clearance calculated by Cockcroft and Gault's formula > 60 mL/min.

- 11. Adequate hematologic status:
 - ANC $\geq 1,500 \text{ cells/mm}^3$
 - Platelet Count $\geq 100,000 \text{ cells/mm}^3$
 - Hemoglobin $\geq 9.0 \text{ g/dL}.$
- 12. At the time of start of treatment, at least 2 weeks must have elapsed since completion of prior chemotherapy, minor surgery, radiotherapy (provided that no more than 25% of bone marrow reserve has been irradiated).

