9.4.4. Retreatment and Dose Delay

A new cycle of treatment may begin when the ANC is $\geq 1500/\text{mm}^3$, the platelet count is $\geq 100,000/\text{mm}^3$, and the non-hematologic toxicities are \leq grade 1, except for alopecia (for which a grade > 1 is allowed) and for ocular toxicity (for which a worsening retinopathy of 1 or more grades compared to baseline implies study treatment discontinuation) or are recovered to baseline values, if grade 2 is allowed at study entry. If these conditions have not been met, treatment should be delayed for 1 or 2 weeks to allow for recovery. If after a maximum of a 2-week delay all toxicities (except for alopecia and for toxicities for which grade 2 is allowed at study entry) are \leq grade 1, then proceed with treatment as outlined in the Dose Modification Table 4. An increased delay > 2 weeks is to be discussed between the Investigators and the Sponsor on a case by case basis.

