11.4.1.5. Recording Adverse Events in the Case Report Forms

Information on adverse events must be evaluated by a physician and recorded in a source document such as the hospital file. Adverse events are to be recorded on the case report forms as above specified. The Investigator will also be asked to assess the relationship between the adverse event and the investigational medication.

• Preexisting Conditions

In this trial, a pre-existing condition (i.e., a disorder present before an adverse event occurs and recorded on the pretreatment medical history/physical examination form) should not be reported as an adverse event unless the condition worsens or episodes increase in frequency during the adverse event reporting period.

• Baseline Signs and Symptoms

Tiziana Life Sciences, PLC - Confidential Page 68 of 101

Milciclib maleate (PHA-848125AC)	CDKO-125a-006-P4
Protocol for Study CDKO-125a-006	09 March 2017

All Signs and Symptoms (either tumor-related or not tumor-related) collected at baseline should not be reported anymore during the study except in case they worsen in severity or in frequency.

• Procedures

Diagnostic and therapeutic non-invasive and invasive procedures, such as surgery, should not be reported as adverse events. However, the medical condition for which the procedure was performed should be reported if it meets the definition of adverse event. For example, an acute appendicitis that begins during the adverse event reporting period should be reported as the adverse event and the resulting appendectomy should be recorded in the source documents.

After cut-off date of 31 May 2017, AE/SAE data will be no longer collected into the CRF, but assessments information should continue to be collected into the patient's medical notes.

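### Laboratory incidence counts each patient's worst on-treatment grade regardless of baseline grade, so unchanged entry abnormalities count as on-treatment abnormalities

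*Protocol*

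**What the plan says.** Section 12.3.6 grades laboratory values by CTCAE version 3.0 where possible. For each graded test, "abnormalities will be evaluated by considering the worst occurrence for each patient throughout the whole treatment period". Nothing in that sentence refers to the grade before treatment.

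The section treats baseline in four other places:

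- Laboratory tests in general: "For selected parameters descriptive analysis of shifts relative to baseline will be performed if deemed of clinical relevance". No parameter is named.
- Coagulation: "Coagulation tests will be evaluated with respect to the corresponding baseline values and to the recorded normal ranges".
- Ophthalmology: "Shift tables comparing patients' worst assessments after treatment initiation to the corresponding baseline assessments will be built".
- Individual listings: "calculation of changes from baseline will be provided in the listings for those parameters and conditions deemed of clinical relevance".

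On entry, criterion 9 of section 6.1 admits raised liver tests, for example "ALP ≤ 2.5 ULN (if liver and/or bone metastases are present, then ≤ 5 ULN is allowed"). Section 9.4.4 lets a new cycle start when non-hematologic toxicities are at most grade 1 "or are recovered to baseline values, if grade 2 is allowed at study entry". The failure-to-recover row of Table 4 makes the same allowance.

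**The concern.** An incidence should describe what arises or worsens on treatment. As written, the laboratory figure mixes abnormalities already present at entry with those that develop later. The patients are pretreated and have recurrent or metastatic disease, so some abnormal baseline values are to be expected. With a single arm, there is no control group from which to read off the background level.

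The table carries weight because of how adverse events are defined. Section 11.4.1.1.1 keeps uncomplicated, asymptomatic laboratory findings out of adverse event reporting unless they lead to discontinuation or need clinical intervention. For silent changes in hematology and chemistry, the worst-grade table is then the only aggregate summary that the protocol guarantees. The shift analysis and the distribution of cycles by worst grade are both limited to selected parameters. Laboratory parameters are part of the overall safety profile, a secondary endpoint in section 4.2.2. The protocol also has reasons to watch change in particular: section 3.2.7 reports occasional prolonged transaminitis on this schedule, and section 9.4.9 includes a fall in creatinine clearance from baseline among its warning signs.

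**Working it through.** The protocol states no figure on this point, so there is none to reproduce. The check sets the entry limits beside the analysis rule and then illustrates the size.

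**Step 1: what can be abnormal at entry, and what is compared with baseline.**

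| Item | Entry limit (sections 6.1, 6.2, 9.4.8) | State possible at entry | Baseline comparison guaranteed in 12.3.6 |
|---|---|---|---|
| AST/ALT | 2.5 ULN; 5 ULN with liver metastases | abnormal | no |
| ALP | 2.5 ULN; 5 ULN with liver and/or bone metastases | abnormal | no |
| Bilirubin | 1.5 ULN | abnormal | no |
| Creatinine | at most ULN, or clearance above 60 mL/min | abnormal through the second branch | no |
| Hemoglobin | at least 9.0 g/dL | abnormal | no |
| Neutrophils | at least 1,500/mm³ | not grade 2 (Table 4: below 1500) | no |
| Platelets | at least 100,000/mm³ | not grade 2 (Table 4: below 75000) | no |
| Electrolytes, amylase, lipase | no numerical limit | not restricted by a limit | no |
| Coagulation tests | coagulation disorders excluded | no numerical limit | yes |
| Retinopathy | grade above 1 excluded | grade 1 | yes, shift tables |

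The last row is the closest parallel. Grade 1 retinopathy is accepted at entry, and the protocol answers with compulsory shift tables. Abnormal liver tests and hemoglobin are accepted too, but a baseline comparison for them is left to discretion.

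**Step 2: which grades are affected.** The protocol does not reproduce the CTCAE limits for liver tests or hemoglobin. The grade 2 point therefore rests on section 9.4.4 and Table 4, neither of which names the items. They contemplate nothing above grade 2 at entry. For tests with an entry limit, grade 3-4 counts should thus be little affected, and the distortion lies in grades 1-2. Tests without a limit have no such protection.

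**Step 3: size, by assumption.** Let N = 60 (the maximum planned enrolment, section 12.1). Let b be the share with an abnormal baseline value that persists without worsening, and q the new-onset rate among those normal at baseline. Neither b nor q is in the protocol.

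- Tabulated any-grade count: N × [b + (1 − b) × q]
- New or worsened count: N × (1 − b) × q
- Excess: N × b

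| b | q | Tabulated | New or worsened | Excess |
|---|---|---|---|---|
| 10% | 0% | 60 × 0.10 = 6 | 0 | 6 |
| 40% | 0% | 60 × 0.40 = 24 | 0 | 24 |
| 10% | 10% | 60 × 0.19 = 11.4 | 60 × 0.09 = 5.4 | 6 |
| 40% | 10% | 60 × 0.46 = 27.6 | 60 × 0.06 = 3.6 | 24 |
| 10% | 30% | 60 × 0.37 = 22.2 | 60 × 0.27 = 16.2 | 6 |
| 40% | 30% | 60 × 0.58 = 34.8 | 60 × 0.18 = 10.8 | 24 |

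The excess does not depend on q. Patients with an abnormal baseline who worsen, or whose on-treatment values are all normal, do not belong in b, so the excess is smaller than N times the entry prevalence to that extent.

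**The case against.** The strongest reply is that section 12.3.6 already plans baseline comparisons: optional shifts, an unconditional comparison for coagulation, and changes from baseline in some listings. On this view, which tests get a shift table is detail for an analysis plan that is not shown, and the unadjusted worst grade is a legitimate descriptive summary.

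Part of this stands. It would be wrong to say that laboratory data are never compared with baseline. But the incidence rule is stated in the protocol and is not a gap left for later. Listings are not an aggregate summary, and their changes from baseline are limited in the same way as the shifts. The unadjusted worst grade is useful beside a shift table; alone, it cannot separate old from new.

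Some stronger readings are tempting and are not supported:

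- A reader might infer that entry abnormalities are reported as drug toxicity. The text says abnormalities. Section 11.4.1.1.1 counts laboratory changes as adverse events only if new or worsened, so the adverse event tables should not absorb unchanged baseline values.
- A reader might infer that grade 2 is allowed at entry for every test. It is not, for neutrophils or platelets.
- A reader might infer that shift parameters will be picked after the data are seen. The protocol does not say when relevance is judged. It leaves this open, and an analysis plan could settle it in advance.
- A reader might see a contradictory analysis rule for clinical signs, since section 11.4.1.5 says that those "collected at baseline should not be reported anymore during the study except in case they worsen in severity or in frequency". That is a recording rule for the case report form, not an analysis rule.
- The liver signal should not be overstated. Section 3.2.7 reports liver test changes as more frequent on a different schedule, 14 consecutive days every 3 weeks.

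**Conclusion.** The point holds in a limited form. For hematology and chemistry, the stated incidence includes abnormalities that were present at entry and did not change, and no baseline comparison is guaranteed in any aggregate table. The consequence is inflated grade 1-2 counts for tests such as liver enzymes and hemoglobin, and possibly inflated counts at any grade for tests without an entry limit.

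The range of 6-24 patients out of 60 rests wholly on an assumed baseline prevalence of 10%-40% that persists unchanged, and on full enrolment. It shows scale and is not an estimate for this trial. No decision rule, stated figure or efficacy conclusion depends on it. This is a cheap improvement to the safety reporting, not a flaw in the design.

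**What to change.** In section 12.3.6, make a table of baseline grade by worst on-treatment grade mandatory for every CTCAE-graded hematology and chemistry test. Count as incident only patients whose worst on-treatment grade exceeds their baseline grade. Keep the unadjusted worst grade as a supplementary column, so that nothing now planned is lost. This brings these tests into line with the rule for ophthalmology in the same section.

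The cost is a little more programming. Sections 7 and 11.4.2 already require hematology and chemistry at baseline and between Days 11 and 14 of each cycle, so no extra visit or sample is needed.
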